- previous history or current diagnosis of neoplasms and/or anti-neoplastic therapies within 5 years from randomization
- history of diabetic ketoacidosis
- current therapies with steroids and/or anti-psychotic medications
- any concomitant conditions which can preclude participation in the study

Female participants in fertile age have to use contraceptives during the study. Moreover, women who meet inclusion criteria will be screened for pregnancy before the completion of the enrollment.

Randomization

Randomization using a computer generated random-number sequence.

Allocation

Concealed in sealed study folders that will be held in a central, secured location until after informed consent will be obtained.

Interventions

LIRA GROUP: participants assigned to LIRA group will start on 0.6 mg once daily liraglutide subcutaneous injection at approximately the same time of the day. The dose will be titrated up on a weekly schedule by 0.6 mg increase to a target dose of 1.8 mg or the maximum tolerated. In accordance with standards of medical care, cardiovascular risk factors will be managed as follows:

systolic blood pressure below 130 mmHg and diastolic blood pressure below 80 mmHg obtained, if needed, with ACE inhibitors or angiotensin receptor blockers, LDL-cholesterol below 70 mg/dL, aspirin therapy at the dosage of 100 mg daily or alternatively clopidogrel 75 mg daily in case of documented aspirin allergy.

CONTROL GROUP: individuals assigned to control group will be given, if needed, tailored therapeutic prescriptions to manage blood glucose levels and cardiovascular risk factors, according to the standards of medical care. The established treatment goals for cardiovascular risk factors control will be: systolic blood pressure below 130 mmHg and diastolic blood pressure below 80 mmHg obtained, if needed, with ACE inhibitors or angiotensin receptor blockers, LDL-cholesterol below 70 mg/dL, aspirin therapy at the dosage of 100 mg daily or alternatively clopidogrel 75 mg daily in case of documented aspirin allergy.

Recruitment and time schedule

Recruitment will last 18 months. Participants will be followed up for 24 weeks (6 months).

Time schedule	Visit 1 (Screening)	Visit 2 (Randomization)	Visit 3 (3 months follow- up)	Visit 4 (End of the study)
	Week -1	Week 0	Week 12	Week 24
Informed consent	x			
Eligibility evaluation	x			
Pregnancy screening test [†]	x			
Start of the intervention		x		

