Anamnesis and clinical assessment	x			
Physical examination: weight, BMI, WC		x	x	x
Blood pressure evaluation		x	x	x
Glycemic profile evaluation: fasting glucose, HbA _{1c}	x	x	x	x
Lipid profile evaluation: total cholesterol, LDL-chol, HDL-chol and triglycerides		x	x	x
Renal function evaluation: creatinine, azotemia, eGFR	x	x	x	x
Inflammation markers: CRP, fibrinogen, TNF- α and IL-6		x		x
Angiogenesis markers: EPCs and VEGF		x		x
Sexual hormones evaluation: testosterone or estradiol, LH, FSH, SHBG*		x		x
Albuminuria		x		x

ABI and 6-minute walking test		x		x
TcPO ₂	x	x	x	x
IIEF-5 questionnaire*		x		x
FSFI questionnaire†				
Adverse events evaluation		x	x	x

*In males; †In females.

ABI, Ankle Brachial Index; BMI, Body Mass Index; CRP, C-reactive protein; EPC, Endothelial Progenitor Cell; eGFR, estimated Glomerular Filtration Rate; FSFI, Female Sexual Function Index; FSH, Follicle-stimulating hormone; IL-6, Interleukin 6; IIEF-5, International Index of Erectile Function 5; LH, Luteinizing hormone; SHBG, Sex hormone-binding globulin; TcPO₂, Transcutaneous Oxygen Pressure; TNF- α , Tumor Necrosis Factor α ; VEGF, Vascular Endothelial Growth Factor; WC, Waist circumference.

Study withdrawal

Subjects may withdraw from the research at any time for:

- voluntary retirement;
- occurrence of adverse event which requires the end of the study;
- poor adherence to trial intervention and/or follow-up;
- modification of inclusion/exclusion criteria from baseline;
- novel treatment with medications interfering with the endpoints evaluation;
- pregnancy.

Investigators may interrupt the research in case of:

- occurrence of adverse events (nausea, vomit, abdominal pain, fever, rush and/or eosinophilia);
- renal function worsening (eGFR <15 mL/min/1.73m²);
- dialysis or renal transplantation;
- chetoacidosis (confirmed by laboratory tests);
- occurrence of acute or chronic pancreatitis;
- medullary carcinoma diagnosis after randomization;
- any adverse event or relevant clinical event, considered as an interference for the research;
- any allergic reactions;
- recruitment of the individual in other study interfering with the research.

Primary outcomes

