The co-primary outcomes of the study are the peripheral perfusion assessed at baseline and at the end of the study and the proportion of individuals who reaches a 10% increase of the TcPO₂ value from the baseline in each group. The change of TcPO₂ of the foot in people treated with liraglutide compared with individuals of the Control group will be calculated after 6 months. The TcPO₂ change will be evaluated as the difference between TcPO₂ values measured at the end of the trial and baseline.

Secondary outcomes

The secondary outcomes of the study are the change (measured as the difference of variables at the end of the trial vs. baseline) in glyco-metabolic, inflammation and angiogenesis, atherosclerosis

parameters in people treated with liraglutide compared with individuals of the Control group. Moreover, we will evaluate the changes in renal function, sexual hormones levels and sexual function.

18-month extension of the follow-up

An 18-month extension of the follow-up will be performed for all the study population, according to guidelines and good clinical practice. The follow-up will include the glyco-metabolic parameters and the main cardiovascular risk factors, including TcPO₂ assessment.

Data from this extended observation will be collected for additional analyses (mostly regarding the durability of the effects). Individuals who will be lost during follow-up and/or discontinue or modify the glucose-lowering treatment will be excluded from the analyses.

Methods

All individuals will be informed about the aims of the study through a specific information letter. Moreover, during the screening visit, we will collect written informed consent and deliver an information letter for the general practitioner of each participant.

Physical examination - Height and weight will be recorded using the Seca 200 scale, with attached altimeter (Seca, Hamburg, Germany). The WC will be measured in orthostatic position, at anterior-superior iliac spine, using a graduated instrument. BMI will be calculated as weight in kg divided by the height in squared meters (kg/m²). Blood pressure will be measured three times, with patients in sitting position, after at least 15 minutes of rest.

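### The withdrawal rules allow participants to leave the research itself over poor adherence or ungraded adverse events, with no TcPO2 required after such an exit, so week-24 values may be lost more from the LIRA arm

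*Protocol*

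**What the plan says.** The Protocol's Study withdrawal section has two lists. In both, what ends is the research rather than the drug.

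- **Participant list.** The grounds include "poor adherence to trial intervention and/or follow-up" and "occurrence of adverse event which requires the end of the study". The adverse-event ground is qualified.
- **Investigator list.** It opens "Investigators may interrupt the research in case of" and includes "occurrence of adverse events (nausea, vomit, abdominal pain, fever, rush and/or eosinophilia". No grade, seriousness or relatedness is attached, although Safety and Adverse Events defines grades 1 to 5. The list also contains "recruitment of the individual in other study interfering with the research", which can only concern one person, so it is read here as ending one participant's involvement.

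Four other places bear on the point.

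- **Recruitment and time schedule** sets 24 weeks of follow-up, and its table places TcPO2 at screening and weeks 0, 12 and 24, for participants in general.
- **Interventions** titrates liraglutide "to a target dose of 1.8 mg or the maximum tolerated", so a reduced dose is within plan and is not at issue. The control group receives standard care, with no placebo or injection.
- **Primary outcomes** fixes the timing: the TcPO2 change is "compared with individuals of the Control group will be calculated after 6 months". The responder co-primary, a 10% rise from baseline, rests on the same measurement.
- **Planned statistical analysis** computes changes from the last observation and allows for 10% dropout, not split by arm.

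**The concern.** Stopping a drug and leaving a trial are different events, and the withdrawal section does not keep them apart. A LIRA participant with nausea, or one who stops injecting, may be taken out of the research, and nothing then calls for another TcPO2 reading. An exit before week 12 leaves no post-baseline value. An exit between weeks 12 and 24 leaves at best a week-12 value in place of the 6-month outcome.

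The arms are not equally exposed. Liraglutide intolerance and non-adherence to the injection can arise only in LIRA. Fever, worsening renal function or an interfering new medication can arise in either arm. If exits do concentrate in LIRA, and those who exit differ in perfusion from those who stay, both co-primary outcomes compare a selected LIRA group with a fuller control group. An analysis plan can choose how to treat missing values, but it cannot supply a week-24 TcPO2 that was never taken. That makes this a matter for the protocol.

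**Working it through.** **The plan's own figure.** Inputs from Planned statistical analysis: SD 5 mmHg, 90% power, α 0.05 (taken as two-sided), 10% dropout, 1:1 allocation, at least 50 participants. The 10% difference is not given in mmHg. Taking it as 4.9 mmHg, which is 10% of the top of the eligible range (30 to 49 mmHg), the normal approximation gives:

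- n per arm = 2 × (1.960 + 1.282)² × 5² / 4.9² = 21.9, so 22
- total 44; 44 / 0.90 = 48.9, so 49, against the stated 50

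The stated size is reproduced on that reading and is not in dispute here. Planned losses are 10% × 50 = 5.

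**Bias from unequal loss (illustration).** Assumed, because the document gives no such figures:

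- no average effect over all 25 randomised to LIRA;
- only observed values are analysed;
- exits occur before week 12;
- in either arm, the lost participants' TcPO2 change would have been g mmHg below that of those retained, with g = 2, 4 or 5.

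If L of the 25 in an arm are lost and the arm's true mean change is 0, the retained mean is g × L/25. Hence bias = g × (LIRA lost − control lost)/25. The standard error for 20 v 25 is 5 × √(1/20 + 1/25) = 1.50 mmHg; for the other splits it is 1.49. The false-positive rate comes from the noncentral t distribution with 43 degrees of freedom, two-sided at 0.05.

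| Losses LIRA : control | Bias, mmHg (g = 2, 4, 5) | False-positive rate (g = 2, 4, 5) |
|---|---|---|
| 5 : 0 | 0.40, 0.80, 1.00 | 5.8%, 8.2%, 10.0% |
| 4 : 1 | 0.24, 0.48, 0.60 | 5.3%, 6.1%, 6.8% |
| 3 : 2 | 0.08, 0.16, 0.20 | 5.0%, 5.1%, 5.2% |

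A simulation of the 5 : 0 row (400,000 runs) gave 5.8%, 8.1% and 10.0%.

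**Responder outcome, 5 : 0 split.** With an assumed baseline of 40 mmHg, a responder gains at least 4 mmHg. Changes are taken as normal with SD 5. The LIRA proportion is overstated by 0.2 × (proportion among retained − proportion among lost):

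- g = 2: 0.2 × (0.236 − 0.131) = 2.1 points
- g = 4: 0.2 × (0.261 − 0.075) = 3.7 points
- g = 5: 0.2 × (0.274 − 0.055) = 4.4 points

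**Power.** At 4.9 mmHg, power is 89.1% with 20 v 25 and 89.5% with the same 5 losses spread as 22 v 23. The issue is bias, not power.

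**The case against.** The strongest reply is that follow-up is already provided. Recruitment and time schedule gives every participant 24 weeks, and the table gives everyone TcPO2 at weeks 12 and 24. The protocol also knows treatment discontinuation as a state of its own: the adverse-event overview counts patients who stop treatment, and the pregnancy rule stops liraglutide while the woman is still monitored. This stands. A reader might infer that nobody who stops liraglutide is due a week-24 TcPO2. The text does not support that, because someone who stops the drug but remains in the research is still on the schedule. The gap concerns people who exit under the withdrawal section.

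Second, the investigator list contains pancreatitis, medullary carcinoma and allergic reactions, and reads much like a set of drug-stopping criteria. That may be what was meant, and the ungraded adverse-event ground would then fall away. The wording says otherwise, however, and the poor-adherence ground in the participant list would remain.

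Third, both lists are permissive. A reader might infer that everyone with nausea or poor adherence is removed; neither list requires it. Nor does the document give loss by arm or link intolerance to perfusion. If those lost would have done better than those retained, the bias would run against liraglutide.

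Fourth, two passages might seem to decide the matter, and neither does. The last-observation rule may keep a week-12 value for later exits, which softens the loss without supplying the 6-month outcome. The rule that participants who "discontinue or modify the glucose-lowering treatment will be excluded from the analyses" belongs to the 18-month extension. It does not exclude anyone from the week-24 comparison.

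**Conclusion.** The point holds as a defect in a conduct rule. The withdrawal section permits exit from the research on grounds that include poor adherence and, as worded, ungraded adverse events, and no TcPO2 is required after such an exit. That losses would fall mainly on LIRA is an inference from the design, not something the protocol states.

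The size is uncertain and probably modest. At a 4 : 1 split it is about half a millimetre of mercury or less for gaps up to 4 mmHg, and 0.60 mmHg at a gap of 5, against a standard error of 1.49 mmHg. A reader might take 1.0 mmHg and a 10.0% false-positive rate as the expected harm. Those figures need every planned loss to be in LIRA, before week 12, with a gap of one full SD, and the documents support none of these as likely. At 3 : 2 the effect is negligible. The point is worth correcting because the correction is cheap and because no later analysis can replace the missing measurements. Confidence is medium, given the ambiguity of the investigator list.

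**What to change.** In Study withdrawal, state that an adverse event or poor adherence ends study drug only, and that TcPO2 is still measured at the scheduled weeks 12 and 24 unless the participant withdraws consent. The same sentence can cover the grounds for a new interfering medication and for a relevant clinical event. If the investigator list was meant as drug-stopping criteria, its opening line should say so.

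The cost is amendment wording only: the visits and measurements are already scheduled, and sample size and eligibility do not change. The small downside is that the estimated effect then includes participants who are off drug. The protocol's closing statement says that the trial ran from February 2021 to December 2022, so a change of wording cannot recover values already missed.

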“Effects of the GLP-1 receptor agonist liraglutide on lower limb perfusion in people with type 2 diabetes and peripheral artery disease: a randomized controlled trial (STARDUST)” is designed to determine the effect of injectable liraglutide on peripheral perfusion in individuals with type 2 diabetes and PAD. Peripheral perfusion will be assessed through the $TcPO_2$ measurement on the foot. Moreover, we will evaluate the effect of GLP-1RAs on parameters of glyco-metabolic control, inflammation, angiogenesis and cardiovascular risk markers. Particularly, we will analyze:

- glyco-metabolic parameters [fasting glucose, glycated hemoglobin (HbA_{1c}), weight, body mass index (BMI), waist circumference, systolic and diastolic blood pressure];
- lipid profile (total cholesterol, LDL cholesterol, HDL cholesterol, triglycerides);
- inflammation markers [C-reactive protein (CRP), fibrinogen, tumor necrosis factor alpha, interleukin-6];
- renal function parameters [creatinine, azotemia, urine albumin to creatinine ratio (UACR), glomerular filtration rate (eGFR)];
- angiogenesis markers [endothelial progenitor cells (EPCs) and vascular endothelial growth factor (VEGF)];
- PAD clinical assessment (ABI, 6-minutes walking test);
- sexual hormones levels and sexual function.

Study design

STARDUST is a single-center, randomized clinical trial lasting 24 weeks. The study will include a screening visit, a randomization visit and 2 follow-up visits (3 month and 6 month).

Study population

Eligibility will be considered for individuals with type 2 diabetes aged > 35 years, PAD diagnosed through doppler ultrasound, angio-CT, angiography in the past 12 months, TcPO₂ value of the foot ranged between 49 and 30 mmHg.

Inclusion criteria

- diagnosis of type 2 diabetes
- HbA_{1c} ranged between 6.5% and 8%
- Glucose-lowering therapy with metformin and/or insulin on stable doses for at least 3 months

Exclusion criteria

- diagnosis of type 1 diabetes
- current or recent treatment with GLP-1RAs and/or DDP-4 inhibitors
- participation to other clinical research, including drug administration
- contraindications to the treatment with GLP-1RAs
- plans for pregnancy or current pregnancy or breast feeding
- history of thyroid disease
- inflammatory bowel disease
- acute coronary and/or cerebravascular disease within the previous 14 days
- plans and/or indications to peripheral revascularization procedure
- estimated glomerular filtration rate (eGFR) below 15 ml/min per 1.73m²

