Assessment of Female Sexual Function – Female sexual function will be studied through the FSFI questionnaire which assesses sexual activity over the past 4 weeks and includes 19 questions. The questionnaire will investigate six distinct domains (sexual desire, arousal, lubrication, orgasm, satisfaction and pain), and provide a total score indicative of global sexual function. A total FSFI score < 26.55 will be used to classify the presence of female sexual dysfunction. The FSFI questionnaire will be administered at visit 2 (week 0) and at the end of the study (week 24).

Evaluation of TcPO₂ - The measurement of transcutaneous oxygen tension will be performed on both limbs of each participant. Anterior tibial artery perfusion will be assessed near the base of the third finger, while posterior tibial artery perfusion will be evaluated near the lateral malleolus. The patients will be examined in supine position, after 20 minutes of rest. The application of the electrodes has to avoid areas with bony prominences, superficial veins or skin lesions. Measurement sites will be cleaned with an alcoholic solution, the electrodes will be fixed to the skin through an adhesive ring, after the application of a contact solution. Before each measurement, the oximeter will be calibrated for at least 10 minutes. The TcPO₂ measurement will be recorded for 16 minutes. According to manufacturer sheet, TcPO₂ value ≥ 50 mmHg is considered as indicator of a normal perfusion, while TcPO₂ value < 30 mmHg is referred to critical ischemia. The lowest value of each participant will be considered for the follow-up and the analysis.

Planned statistical analysis

The sample size calculation was performed based on the change of the primary endpoint (change in $TcPO_2$). Assuming an estimated standard deviation of 5 mmHg, a dropout rate of 10%, we expect to require at least 50 participants (in a 1:1 ratio LIRA:Control strategies) to achieve the 90% power to detect an 10% difference between group at a α -level of 0.05.

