Descriptive statistics will be used for demographic and baseline clinical characteristics of all participants in the study. Continuous variables will be described as either mean and standard deviation (SD) or medians and interquartile range (IQR) according to sample distribution, and count data will be reported as numbers and percentages. Comparisons of baseline data between groups will be performed by Student's t test or Mann-Whitney Rank Sum test, depending on the normality of sample distribution. Comparison among frequencies was made with the χ^2 test.

To evaluate the change of variables over time Δ values will be calculated as value at the last observation minus value at the start. The paired t test and Wilcoxon signed rank test within each patients' group will be used to assess changes in the studied variables from baseline to the last observation. Two-sample t-test will be used to compare differences between interventions. The χ^2 test will be used for comparing proportions of participants in the 2 groups who reached the primary endpoint after the intervention. Relative Risk (RR) and 95% confidence interval (CI) will be calculated to demonstrate the relationship between the intervention and the achievement of the primary endpoint. Data were also analyzed by analysis of variance for repeated measures with a post-hoc comparisons made with the Scheffé's test. P value < 0.05 will be considered statistically significant. All analyses will be conducted using SPSS version 19.0 (SPSS Inc, Chicago, Ill).

Safety and Adverse Events

Adverse event (AEs) - Any unexpected event occurred in a patient included in a clinical trial after the administration of a pharmacological product. This event is not necessarily related to pharmacological treatment. Therefore, an AE, may be any unpleasant and unwanted clinical sign (for example, an abnormal laboratory finding), symptom, or disease, which is transiently associated with the use of a drug. According to the guidelines of the Common Terminology Criteria for Adverse Events (<https://www.fda.gov/downloads/Guidances/UCM174090.pdf>), AEs will be divided in different grades.

- Grade 1 (mild): lack of symptoms or mild symptoms, with no indication to specific intervention; clinical or diagnostic observation is required.
- Grade 2 (moderate): moderate symptoms requiring local or non-invasive intervention; it may determine a limitation of daily activities.

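### TcPO₂ is read at week -1 and at week 0, but the baseline of both co-primary outcomes is tied to neither visit and no stated rule uses both; averaging them would gain precision at almost no cost

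*Protocol*

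**What the plan says.** The time schedule in the Protocol (Recruitment and time schedule) marks TcPO₂ at all four visits: weeks -1, 0, 12 and 24. The row "Start of the intervention" is marked at week 0, and eligibility is evaluated at week -1. Under Study population, eligibility requires a TcPO₂ "value of the foot ranged between 49 and 30 mmHg".

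Under Primary outcomes, the change is the difference between "values measured at the end of the trial and baseline". The second co-primary outcome is "the proportion of individuals who reaches a 10% increase of the" TcPO₂ value from baseline. Planned statistical analysis defines Δ as "value at the last observation minus value at the start". Each phrase points to one starting value, and none names a visit.

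The only selection rule is in Methods, Evaluation of TcPO₂: "The lowest value of each participant will be considered for the follow-up and the analysis". It follows the description of two sites on each limb and does not mention visits.

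**The concern.** Each participant should have two TcPO₂ readings about a week apart, both up to the start of treatment. A single reading carries its full measurement error into the change score, and it also sets that participant's 10% hurdle. Averaging two readings halves the error variance of the baseline.

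This matters more in a trial of 50. The stated size reproduces only if the 10% difference means about 5 mmHg, at the top of the eligibility window. For a smaller difference, power is well below 90%.

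Leaving the visit open has a second consequence: week -1, week 0, their mean, or even the lower of the two could each be called baseline, and they behave differently.

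**Working it through.** **Inputs from the Protocol.** Planned statistical analysis gives "Assuming an estimated standard deviation of 5 mmHg, a dropout rate of 10"%, 50 participants in a 1:1 ratio, 90% power and α 0.05. I take the SD of 5 as that of the change, because the sizing is on the change, and I take the test as two-sided. Evaluable: 50 × 0.9 = 45, or 22.5 per arm.

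**The plan's own figure.** With a difference of 5 mmHg, n per arm = 2 × (1.96 + 1.2816)² × 5² / 5² = 21.0, taken as 22. Then 22/0.9 = 24.4, so 25 per arm and 50 in total, which reproduces. At 3.95 mmHg (10% of the window midpoint, 39.5) the formula gives 33.7, so 34 per arm, 38 after dropout and 76 in total.

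**Variance of the change.** Let s² be the variance of one reading, r the correlation of either pre-treatment reading with week 24, and r₁₂ the correlation of week -1 with week 0. None of these is in the documents, so they are assumptions.
- One reading as baseline: 2s²(1 − r).
- Mean of two: s²[1 + (1 + r₁₂)/2 − 2r].
- Equal correlations (r₁₂ = r): ratio 1.5(1 − r) / 2(1 − r) = 0.75, whatever r is.
- r₁₂ = 0.9, r = 0.8: 0.35/0.40 = 0.875.
- r₁₂ = 0.95, r = 0.7: 0.575/0.60 = 0.958.

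Put another way, if a share f of the change variance is reading error, the ratio is 1 − f/4. For f = 100%, 50% and 18% this is 0.75, 0.875 and 0.955.

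**Power of the two-sample t-test on change.** Exact t, 22.5 per arm, noncentrality d / (SD × √(2/22.5)):

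| Baseline | SD of change | Power, 5 mmHg | Power, 4 mmHg |
|---|---|---|---|
| One reading | 5.00 | 90.6% | 74.6% |
| Mean of two, f = 100% | 4.33 | 96.6% | 85.7% |
| Mean of two, f = 50% | 4.68 | 93.9% | 80.1% |
| Mean of two, f = 18% | 4.89 | 91.8% | 76.5% |

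A simulation with true-level SD 6 and the screening reading restricted to 30-49 gives SDs of 4.28, 4.67 and 4.88. Power for 4 mmHg is then 87%, 80% and 77%.

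**Responder outcome.** This uses the same simulation with source mean 40. Power is a normal approximation for a true shift of 5 mmHg against none; simulated values with the mean are slightly lower (81%, 76%, 72%).

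| f | Power: week 0, then mean | Responders with no true change: week 0, then mean |
|---|---|---|
| 100% | 68%, 83% | 22.5%, 18.5% |
| 50% | 70%, 77% | 22.0%, 20.1% |
| 18% | 72%, 74% | 21.6%, 21.0% |

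The fall in false responders is small or absent when error is low or the source mean is high: at source mean 45 and f = 18% it is 20.0% to 19.8%.

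**Cost of using the eligibility reading.** With no treatment effect, averaging produces an apparent within-arm change of below 0.1 mmHg at source mean 40. At 45 it is 0.38 (f = 100%) or 0.20 (f = 50%), and at 50 it is up to 0.8. The shift is the same in both arms. Week 0 alone gives about 0.

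**If the lowest-value rule were applied across visits.** At source mean 40, apparent change with no effect would be +2.0, +1.4 and +0.9 mmHg for the three values of f. Responders with no true change would be 35%, 31% and 27%.

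**The case against.** A reader might infer that the protocol uses one reading and throws the other away. That is the natural reading of a singular starting value, but the text does not say it. No visit is named, and the repeated-measures analysis of variance does not list the visits it includes. A statistical analysis plan, not shown, may settle the matter. This part of the objection stands, so the point is limited to a baseline that is not tied to a visit and two readings that no stated rule combines. It still belongs at protocol level, because the protocol itself writes the outcome definition, the Δ formula and the value-selection rule.

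A reader might also infer that the sample size or the test is wrong. Neither follows: a single pre-treatment baseline is valid with correct type I error, and 50 reproduces on its own terms.

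The size of the gain rests on assumptions. The largest figures need all change variance to be reading error, and readings a week apart may be more alike than readings 24 weeks apart, which leaves a gain of only 4% to 12.5% in variance. Adjusting for one baseline reading would recover part of the precision anyway, with a variance ratio to the change score of (1 + r)/2, or 0.65 to 0.90 for r = 0.3 to 0.8. The second reading then saves a further 2% to 20%. The protocol states no such adjustment.

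Finally, the lowest site may differ between the two visits, so the mean can mix sites. That is true, but the same already holds between baseline and week 24 if the rule is applied at each visit.

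**Conclusion.** The point holds as an efficiency improvement. TcPO₂ is scheduled twice up to the start of treatment, the baseline of both co-primary outcomes names no visit, and nothing stated uses both readings. Averaging would cut the variance of the change by about 4% to 25%. Power for 4 mmHg with 45 evaluable would rise from about 75% to 77-87%, with a gain in responder power as well.

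This assumes that the planned SD of 5 is the SD of the change, that the week 0 reading precedes the first dose, and the stated range of reliabilities. The between-arm comparison stays unbiased. The within-arm change does not quite: it can shift by about 0 to 0.4 mmHg for source means of 40 to 45, and up to 0.8 at 50.

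**What to change.** Add one sentence to Primary outcomes, and match the Δ definition to it. For the between-arm comparison of both co-primary outcomes, baseline TcPO₂ is the mean of the week -1 and week 0 values. Each is the lowest value over limbs and sites within that visit, never the lowest across visits. If one is missing, the other is used.

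The within-arm paired tests should keep the week 0 value or carry a note on regression to the mean from the eligibility window. The same note applies to responder rates reported for each arm.

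No new visit or measurement is needed. The change has to be fixed before outcome data are seen. The protocol's closing note says that the trial ran from February 2021 to December 2022, so if the analysis has already been done, the averaged baseline belongs in a labelled sensitivity analysis. The report should then state which visit supplied the baseline.

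### The extension's only stated analysis rule drops everyone lost and everyone whose glucose-lowering treatment changes, so durability is described only in a subset selected after randomisation

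*Protocol*

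**What the plan says.** The protocol section on the 18-month extension makes three statements that have to be read together.

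- Who is followed: "An 18-month extension of the follow-up will be performed for all the study population". The same sentence places this follow-up under guidelines and good clinical practice.
- What is measured: "The follow-up will include the glyco-metabolic parameters and the main cardiovascular risk factors", with TcPO₂ included. The Aims list fasting glucose and HbA1c among the glyco-metabolic parameters. The stated use of the data is additional analyses, mostly of durability.
- Who is analysed: "Individuals who will be lost during follow-up and/or discontinue or modify the glucose-lowering treatment will be excluded from the analyses".

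No other section sets an analysis population for the extension. The planned statistical analysis gives general tests and a change defined as last observation minus start. It does not mention the extension or bring the excluded participants back. The scheduled follow-up and the visit table end at week 24.

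**The concern.** The rule selects participants on events that happen after randomisation. A participant may stop or change therapy because of intolerance, worsening glucose or a new clinical problem, and each of these can depend on the assigned arm. Those who remain are no longer the randomised groups.

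Two features make the selection more than a formality. First, care under guidelines can itself call for a change of therapy, and that change removes the participant. The Interventions section also allows controls individually adjusted glucose management when required, so treatment adjustment is part of the control strategy as well as a ground for exclusion. Second, for the glycaemic outcomes the trigger is closely tied to the outcome: a participant whose control deteriorates is a likely candidate for a treatment change, and so for removal from an analysis of whether control lasts.

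What counts as modifying treatment is not defined. At entry participants take metformin and/or insulin, so even a small insulin adjustment might exclude someone.

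At stake is the stated purpose of the extension. Within-arm results would describe only the subset on unchanged treatment, and any between-arm comparison would be open to selection bias of unknown direction. Values collected on people who changed therapy would be discarded from a trial planned for about 50.

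**Working it through.** The protocol gives no figure that depends on this rule, so there is none to reproduce. The finding rests on the text; the arithmetic below only shows what the rule could do under stated assumptions.

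**Inputs from the protocol (Planned statistical analysis)**
- SD 5 mmHg. This is a planning value for the 24-week change, carried over here to the extension.
- 50 participants, 1:1, 10% dropout: 50 × 0.9 / 2 = 22.5 per arm.

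**Assumptions (not in the protocol)**
- Fraction excluded per arm, f: 10–50%.
- Absolute correlation, r, between the tendency to be excluded and TcPO₂ change: 0.3–0.5.
- Both follow a latent normal model.

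**Formulas**
- z = Φ⁻¹(f) and λ = φ(z)/(1 − f)
- absolute shift of the arm mean = r × SD × λ
- retained SD = SD × √(1 − r² λ(λ − z))
- SE of a between-arm difference = retained SD × √(2/n), with n = 22.5 × (1 − f)

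**Shift of one arm's mean change (mmHg)**

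| f | λ | r = 0.3 | r = 0.5 |
|---|---|---|---|
| 10% | 0.1950 | 0.29 | 0.49 |
| 20% | 0.3500 | 0.52 | 0.87 |
| 30% | 0.4967 | 0.75 | 1.24 |
| 40% | 0.6439 | 0.97 | 1.61 |
| 50% | 0.7979 | 1.20 | 1.99 |

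For example, at f = 50% and r = 0.5: 0.5 × 5 × 0.7979 = 1.99. A simulation with 4,000,000 draws gave the same shifts at f = 50% (1.20 and 1.99) and retained SDs of 4.86 and 4.58, as the formula does. With r = 0 there is no shift.

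**If the arms were compared**, the bias is the difference between the two arm shifts.
- Equal rates and equal r: essentially zero.
- Equal rates but r = 0.3 in one arm and 0.5 in the other: 0.49 − 0.29, which is 0.19 before rounding, at f = 10%; 1.24 − 0.75 = 0.50 (unrounded inputs) at 30%; 1.99 − 1.20 = 0.80 at 50%.
- Unequal rates, 20% against 40%, with the same r: about 0.4 (r = 0.3) or 0.7 (r = 0.5). Swapping the rates between arms reverses the sign.

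**Precision of a difference**
- No exclusion: 5 × √(2/22.5) = 1.49, 95% half-width 1.96 × 1.49 = 2.92.
- 10% excluded in both arms (n = 20.25): SE 1.55 (r = 0.3, retained SD 4.94) or 1.51 (r = 0.5, retained SD 4.82).
- 50% excluded in both arms (n = 11.25): SE 2.05 (retained SD 4.86) or 1.93 (retained SD 4.58), half-width 3.79–4.01.

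The rule causes only part of this loss of precision, because people who are lost have no later values under any rule. The base of 22.5 per arm already removes the planned 10% dropout, so losses may be counted partly twice if f also includes them.

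**Scale.** Ten per cent of the eligible baseline TcPO₂ range of 30–49 mmHg is 3.0–4.9 mmHg.

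**The case against.** The strongest reply is that these analyses lie outside the trial's declared outcomes. The co-primary and secondary outcomes end at 24 weeks, and the extension has no named endpoint, test or sample size. No between-arm extension comparison is named, so the between-arm bias and SE figures apply only if one is made. All of this is correct, and it limits the weight of the point. It does not remove it: durability is the extension's stated purpose, and this is the only analysis rule the protocol gives for it.

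It can also be said that durability under unchanged treatment is a coherent question, and that an all-randomised analysis answers a different one. That is also true, and the protocol does not say whether assigned treatment is maintained after week 24. The fault is that the restricted analysis stands alone, although everyone is to be followed.

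The SAP is not at hand and might add further analyses. That possibility does not cure an exclusion which the protocol itself fixes.

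Finally, those lost have no later values, and no interim extension visits are stated, so they may contribute little beyond their data to week 24. This stands. The avoidable part of the problem is mainly the removal of people who stay in follow-up but change therapy.

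**Conclusion.** The concern holds. Followed as written, the rule yields a durability result for a subset selected after randomisation, and for the glycaemic outcomes the selection is closely tied to the outcome itself. This is clear from the text and needs no assumption.

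The size is not known. Under the assumed exclusion rates, correlations and SD, an arm's mean TcPO₂ change could shift by about 0.3–2.0 mmHg in either direction, and by nothing if exclusion is unrelated to the outcome. Neither the sign nor the size can be fixed from the protocol. The 24-week results are not touched. The rule should be corrected, but it does not threaten the trial's main conclusions.

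**What to change.** Replace the exclusion sentence with the following.

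1. The main extension analysis includes all randomised participants in their assigned group and uses all collected values, whether or not glucose-lowering treatment was discontinued or modified.
2. It uses a likelihood-based repeated-measures model, so that those lost contribute their values up to loss, with missing at random stated as the assumption.
3. Losses and treatment changes are reported by arm.
4. The unchanged-treatment subset is kept as a labelled supportive on-treatment analysis, with a definition of what counts as modification and over which period.
5. The extension TcPO₂ time points used by the model are stated.

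The cost is low, because the whole study population is already to be followed. It is more than a change of wording, since the visit table stops at week 24 and the extension time points have to be added. The all-randomised estimate concerns the effect of initial assignment and may dilute an on-treatment effect, which is the reason for keeping the supportive analysis. The missing-at-random assumption for those lost cannot be verified from the data.
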